### 9.9 Analysis of Biological and Correlative Endpoints

The association between the host immune system and response to XL184 will be assessed in an exploratory manner. Immune biomarkers will be divided at their observed median at baseline, Cycle 2 Day 1 (pre dose), and Cycle 3 Day 1 (pre dose), as well as with respect to change from baseline. Then, each biomarker will be correlated with the clinical outcomes of objective response and progression free survival.

Objective response will be assessed using the exact conditional test of proportions and progression-free survival will be assessed using the Log-rank test with hazard ratios estimated from a Cox proportional hazards regression model.

## 10.0 EVALUATION CRITERIA

### 10.1 Common Terminology Criteria for Adverse Events (CTCAE)

This study will utilize the CTCAE of the National Cancer Institute (NCI) for toxicity and performance reporting. The descriptions and grading scales found in the revised CTCAE version 5.0 will be utilized for reporting. All appropriate treatment areas should have access to a copy of the CTCAE version 5.0, which can be downloaded from the CTEP web site ([http://ctep.cancer.gov/protocolDevelopment/electronic\\_applications/ctc.htm](http://ctep.cancer.gov/protocolDevelopment/electronic_applications/ctc.htm)). Additionally, toxicities are to be reported on the appropriate case report forms.

### 10.2 Response Criteria

As outlined, patients will be assigned to one of the following categories for assessment of response: solid tumor and measurable disease ([Section 10.3](#) below). Note: Neuroblastoma patients who do not have MIBG positive lesions or bone marrow involvement should be assessed for response as solid tumor patients with measurable disease.

### 10.3 Response Criteria for Patients with Solid Tumors (non-CNS)

Response and progression will be evaluated in this study using the revised Response Evaluation Criteria in Solid Tumors (RECIST) guideline (version 1.1). Key points are that 5 target lesions are identified and that changes in the *largest* diameter (unidimensional measurement) of the tumor lesions are used in the RECIST v 1.1 criteria.

#### 10.3.1 Measurable Disease

The presence of at least one lesion that can be accurately measured in at least one dimension with the longest diameter at least 10 mm (CT scan slice thickness no greater than 5 mm). The investigator will identify up to 5 measurable lesions to be followed

for response. Previously irradiated lesions must demonstrate clear evidence of progression to be considered measurable.

Serial measurements of lesions are to be done with appropriate imaging modalities, e.g., CT or MRI. Bone scans cannot be used to measure lesions. The same method of assessment is to be used to characterize each identified and reported lesion at baseline and during follow-up.

#### 10.3.2 Quantification of Disease Burden

The sum of the longest diameter (LD) for all target lesions will be calculated and reported as the disease measurement.

#### 10.3.3 End-of-Cycle Response

Note: Please also see Table 1 in [Section 10.6](#).

##### a) Complete Response (CR)

Disappearance of all target and non-target lesions. Normalization of urinary catecholamines (for patients with neuroblastoma), or other tumor markers if abnormal or elevated at study enrollment.

##### b) Partial Response (PR)

At least a 30% decrease in the disease measurement, taking as reference the disease measurement done to confirm measurable disease at study enrollment. No new lesions or progression of any non-target measurable lesion.

##### c) Stable Disease (SD)

Neither sufficient shrinkage to qualify for PR nor sufficient increase to qualify for PD taking as reference the smallest disease measurement since the treatment started.

##### d) Progressive Disease (PD)

At least a 20% increase in the sum of the disease measurements for measurable lesions, taking as reference the smallest disease measurement recorded since the start of treatment, or the appearance of one or more new lesions.

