## 3.2 Eligibility: Inclusion Criteria

**Important note: The inclusion criteria listed below are interpreted literally and cannot be waived. All clinical and laboratory data required for determining eligibility of a patient enrolled on this trial must be available in the patient's medical/research record. These source documents must be available for verification at the time of audit.**

**All clinical and laboratory studies to determine eligibility must be performed within 7 days prior to enrollment unless otherwise indicated. Laboratory values used to assess eligibility must be no older than seven (7) days at the start of therapy. Laboratory tests need not be repeated if therapy starts within seven (7) days of obtaining labs to assess eligibility. If a post-enrollment lab value is outside the limits of eligibility, or laboratory values are > 7 days old, then the following laboratory evaluations must be re-checked within 48 hours prior to initiating therapy: CBC with differential, bilirubin, ALT (SGPT) and serum creatinine. If the recheck is outside the limits of eligibility, the patient may not receive protocol therapy and will be considered off protocol therapy. Imaging studies, bone marrow biopsy and/or aspirate, if applicable, must be obtained within 2 weeks prior to start of protocol therapy (repeat the tumor imaging if necessary).**

3.2.1 Age: Patients must be  $\geq 2$  and  $\leq 30$  years of age at the time of study entry for all strata except upper age limit of  $\leq 18$  years of age for MTC, RCC and HCC.

3.2.2 Body Surface Area (BSA): Patients must have a body surface area  $\geq 0.35$  m^2.

3.2.3 Diagnosis: Patients must have recurrent or refractory disease, or newly diagnosed disease with no known curative therapy or therapy proven to prolong survival with an acceptable quality of life. Patients must have had histologic verification of one of the malignancies listed below at original diagnosis or at relapse.

- Ewing sarcoma
- Rhabdomyosarcoma (RMS)
- Non-rhabdomyosarcoma soft tissue sarcomas (STS) including microphthalmia transcription factor associated STS (alveolar soft part sarcoma (ASPS) and clear cell sarcoma (CCS))
- Osteosarcoma
- Wilms tumor
- Rare tumors
  - Medullary thyroid carcinoma (MTC)

- Renal cell carcinoma (RCC)
- Hepatocellular carcinoma (HCC)
- Hepatoblastoma
- Adrenocortical carcinoma

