### 3.2.4 Disease Status

#### 3.2.4.1 Patients must have radiographically measurable disease.

Measurable disease is defined as the presence of at least one lesion on MRI or CT scan that can be accurately measured with the longest diameter a minimum of 10 mm in at least one dimension (CT scan slice thickness no greater than 5 mm).

Note: The following do NOT qualify as measurable disease:

- malignant fluid collections (e.g., ascites, pleural effusions)
- bone marrow infiltration
- lesions only detected by nuclear medicine studies (e.g., bone, gallium or PET scans)
- elevated tumor markers in plasma or CSF
- previously radiated lesions that have not demonstrated clear progression post radiation
- leptomeningeal lesions that do not meet the measurement parameters noted above.

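### Sections 10.3.3(c) and (d) measure growth from the smallest on-treatment value, so as written tumor growth between the baseline scan and the first follow-up scan cannot count as progression

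*Combined protocol and SAP*

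**What the plan says.** Section 10.3.3(d) sets the growth threshold at a 20% rise in the target sum, "taking as reference the smallest disease measurement recorded since the start of treatment, or the appearance of one or more new lesions". New lesions are thus the alternative route to PD. Section 10.3.3(c) defines stable disease with the matching reference, "taking as reference the smallest disease measurement since the treatment started". Section 10.3.3(b) does name the baseline scan for partial response: "taking as reference the disease measurement done to confirm measurable disease at study enrollment".

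Under section 3.2, imaging "must be obtained within 2 weeks prior to start of protocol therapy", and section 4.2.2 places the baseline tumor evaluation before Cycle 1. Section 10.6 counts evaluations from the first scan after treatment has been given. Sections 4.3.2 and 4.4.2 schedule that scan at the end of Cycle 2 and the next one before Cycle 5. Table 1 in section 10.6 lists progression as a possible first status.

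Section 10.3.3(d) gives no minimum increase in millimeters. A single lesion qualifies as measurable disease with a "longest diameter a minimum of 10 mm in at least one dimension (CT scan slice thickness no greater than 5 mm"). Section 10.3 says that response and progression are evaluated by RECIST v1.1. The CNS rule in section 10.7.2 also takes its PD reference from the start of treatment without naming baseline.

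**The concern.** The authors named the enrollment scan where they wanted it (partial response) and used different words for stable and progressive disease. A site or central reader who follows 10.3.3 literally has no earlier value with which to compare the end-of-Cycle-2 scan. The comparison lost is the one that shows whether the tumor grew over the first two cycles.

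The outcomes most exposed rest on stable disease or on the date of progression. Section 9.3.2 counts at least stable disease, at four months or the end of the sixth cycle, as an osteosarcoma disease control success, and that count enters the go/no-go rule in section 9.2.2. Progression-free survival and time to progression are secondary aims in every stratum. PD is also a criterion for removal from protocol therapy in section 8.1. Response counts are less exposed because partial response is tied to enrollment.

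The lack of an absolute minimum pulls the other way in small tumors, where a change of 2 mm can be PD. The two matters interact, because widening the reference increases the chance of a false call.

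**Working it through.** **1. The rule as written.** Let b be the pre-treatment sum and m1, m2 the sums at the end of Cycle 2 (day 56) and before Cycle 5 (about day 112).

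- First scan: no earlier on-treatment value exists, so the 20% condition cannot be met for any m1.
- Second scan: PD on growth requires m2 ≥ 1.2 × m1. The value of b plays no part.

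| b, m1, m2 (mm) | As written | Baseline in the reference |
|---|---|---|
| 50, 70, 80 | SD, SD (80/70 = +14%) | PD at first scan (70/50 = +40%) |
| 50, 65, 77 | SD, SD (77/65 = +18%) | PD at first scan (+30%) |
| 50, 100, 119 | SD, SD (119/100 = +19%) | PD at first scan (+100%) |

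In the first row the final sum is 80/50 = +60% over baseline, still stable about day 112, and so a disease control success in osteosarcoma. PD at that scan would need 1.2 × 70 = 84 mm, which is +68% over baseline. Even then the PD date would fall at about day 112 instead of day 56.

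**2. What this could do to the osteosarcoma decision.** I first reproduced the design in section 9.2.2 exactly: 19 patients, stop if disease control successes ≤ 4 and responders ≤ 1; then 10 more, effective if successes ≥ 9 or responders ≥ 5, with Pr(S | R) = 0.90. At P(S) = 0.20 and P(R) = 0.05 the per-patient cells are:

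- both: 0.05 × 0.90 = 0.045
- response only: 0.005
- disease control only: 0.20 − 0.045 = 0.155
- neither: 0.795

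The probability of declaring the drug effective is 0.108 (plan: 0.11), and of stopping after stage 1 it is 0.564 (plan: 0.56). The other three scenarios give 0.949, 0.904 and 0.789 (plan: 0.95, 0.904, 0.79).

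The documents do not give the share of patients whose growth would be missed. As a sensitivity range, suppose missed growth lifts the apparent P(S) while the drug is in truth at the null, P(R) = 0.05:

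| Apparent P(S) | P(declare effective) |
|---|---|
| 0.20 | 0.108 |
| 0.25 | 0.275 |
| 0.30 | 0.500 |
| 0.35 | 0.712 |

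**3. The missing minimum.** As written, 10, 10, 12 mm is PD at the second scan: 12/10 = +20%, a 2 mm change. (10 mm at baseline and 12 mm at the first scan is not PD as written, for the reason in step 1.) From a smallest value of 5 mm, 1 mm is enough.

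To see how adding baseline changes chance PD, assume a truly unchanged sum L and independent normal measurement error with SD s at each scan. For one comparison of a later with an earlier value, P(later ≥ 1.2 × earlier) = Φ(−0.2L / (s√(1 + 1.2²))). With L = 10 and s = 1.0 this is Φ(−2/1.562) = Φ(−1.28) = 10.0%. Using the running minimum as reference, simulation gives the cumulative chance of false PD:

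| L, s (mm) | Baseline excluded: by scan 2 / scan 3 | Baseline included: by scan 2 / scan 3 |
|---|---|---|
| 10, 0.5 | 0.5% / 1.5% | 1.5% / 2.7% |
| 10, 1.0 | 10% / 23.5% | 23.5% / 37% |
| 10, 1.5 | 20% / 42% | 42% / 61% |
| 20, 1.0 | 0.5% / 1.5% | 1.5% / 2.7% |

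The values of s are assumptions; the documents give none.

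**The case against.** The strongest reply is that nobody would read the rule this way. Section 10.3 names RECIST v1.1 as the standard, section 10.3.1 asks for the same method at baseline and follow-up, and Table 1 in 10.6 allows progression at the first evaluation, so the authors surely meant the first scan to be compared with baseline. As to intent, that is probably right. It does not settle the text. Section 10.3.3 writes out its own rule and does not defer to the guideline for the reference. Table 1 is not decisive, because a new lesion would also give progression as a first status. Two readers could therefore classify the same scans differently.

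A second reply is that other routes to PD remain. New lesions count at any scan, sections 4.3.2 and 4.4.2 let the investigator call progression on clinical or laboratory evidence, and section 7.3 sends osteosarcoma patients with four or more cycles of stable disease to central review. These narrow the gap. They do not close it for measured growth, and section 7.3 states no different reference for central review.

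On the missing minimum, the objections largely stand. The false-PD figures describe one lesion at the entry limit; up to five lesions are summed, and a 20 mm sum with the same SD shows about 1.5% by the second scan even with baseline included.

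Three stronger inferences are tempting and are not supported:

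- **That the CNS section has a slice-thickness safeguard which the non-CNS section lacks.** A 10 mm lesion on slices of at most 5 mm is the same two-to-one ratio, and the CNS rule has no absolute growth minimum either.
- **That 10.3.3 departs from RECIST v1.1.** The guideline's text is not in the documents, so this cannot be shown from them.
- **That the minimum should be 5 mm because that is the slice limit.** The documents do not link slice thickness to error in the longest diameter.

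**Conclusion.** The reference in 10.3.3(c) and (d) is wrong as written and should be corrected. Literally applied, no amount of target-lesion growth before the end-of-Cycle-2 scan is PD, and a sum that has risen 60% from baseline can count as osteosarcoma disease control. The direction is clear: disease control is overstated, and progression-free survival and time to progression are lengthened. The size is not known. The rise from 0.108 to between 0.275 and 0.712 in the chance of declaring an inactive drug effective rests on an assumed apparent P(S) of 0.25 to 0.35, and on the 0.20 benchmark having been measured with baseline in the reference, which the documents do not say. It is not an estimate of what will happen.

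The missing absolute minimum is a lesser, separate matter. A reader might infer that the present rule gives 23.5% false PD by the second scan in an unchanged 10 mm lesion. It does not: that figure needs baseline in the reference. As written it is 10% at the same assumed 1.0 mm SD. The 23.5% shows what the necessary correction does if made alone. The documents support asking whether a minimum applies; they do not support a particular value.

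**What to change.** 1. In 10.3.3(c), 10.3.3(d) and the CNS PD rule in 10.7.2, state that the reference is the smallest measurement on study, including the pre-treatment baseline. Where imaging was repeated before therapy, say which scan is the baseline.
2. In the same revision, reconcile 10.3.3(d) with the RECIST v1.1 guideline that section 10.3 names, and state whether an absolute minimum increase applies. Because PD leads to removal from protocol therapy under section 8.1, any such value is for the sponsor to settle against that guideline.
3. Give sites and central review the same text, and have scans already classified as stable at the end of Cycle 2 checked against baseline.

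The cost is a few words in two sections and a check of existing measurements. No scan is added, and the sample sizes and decision rules stay as they are.

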#### 10.3.4 Overall Best Response Assessment

Each patient will be classified according to their “best response” for the purposes of analysis of treatment effect. Best response is determined from the sequence of the objective statuses described in [Section 10.6](#).

### 10.4 **Response Criteria for Neuroblastoma Patients with I-MIBG Positive Lesions**

#### 10.4.1 MIBG Positive Lesions

Patients with measurable disease who have a positive MIBG scan at the start of therapy should also be evaluable for MIBG response. The use of I for MIBG imaging is recommended for all scans.

#### 10.4.2 The following criteria will be used to report MIBG response by the treating institution:

- **Complete Response:** Complete resolution of all MIBG positive lesions
- **Partial Response:** Resolution of at least one MIBG positive lesion, with persistence of other MIBG positive lesions.

- **Stable Disease:** No change in MIBG scan in number of positive lesions (includes patients who have same number of positive lesions but decreased density).
- **Progressive Disease:** Development of new MIBG positive lesions.

[figure not shown]
10.4.3 The response of MIBG lesions will be assessed on central review using the Curie scale as outlined below. Central review responses will be used to assess efficacy for study endpoint. See [Section 7.3](#) for details on transferring images to the Imaging Research Center.

NOTE: This scoring is NOT required to be done by the treating institution for end of course response assessments.

The body is divided into 9 anatomic sectors for osteomedullary lesions, with a 10th general sector allocated for any extra-osseous lesion visible on MIBG scan. In each region, the lesions are scored as follows. The **absolute extension score** is graded as:

- 0 = no site per segment,
- 1 = 1 site per segment,
- 2 = more than one site per segment,
- 3 = massive involvement (>50% of the segment).

The **absolute score** is obtained by adding the score of all the segments. See diagram of sectors below:

The **relative score** is calculated by dividing the absolute score at each time point by the corresponding pre-treatment absolute score. The relative score of each patient is calculated at each response assessment compared to baseline and classified as below:

1. **Complete response:** all areas of uptake on MIBG scan completely resolved. If morphological evidence of tumor cells in bone marrow biopsy or aspiration is present at enrollment, no tumor cells can be detected by routine morphology on two subsequent bilateral bone marrow aspirates and biopsies done at least 3 weeks apart to be considered a **Complete Response**.
2. **Partial response:** Relative score  $\leq 0.2$  (lesions almost disappeared) to  $\leq 0.5$  (lesions strongly reduced).
3. **Stable disease:** Relative score  $> 0.5$  (lesions weakly but significantly reduced) to 1.0 (lesions not reduced).
4. **Progressive disease:** New lesions on MIBG scan

10.4.4 Overall Best Response Assessment

Each patient will be classified according to their “best response” for the purposes of analysis of treatment effect. Best response is determined from the sequence of the objective statuses described in Table 2 in [Section 10.6](#).

10.5 **Response Criteria for Neuroblastoma Patients with Bone Marrow Involvement**

10.5.1 Bone Marrow Involvement

Bone Marrow response is determined by H&E staining of bilateral bone marrow biopsies and aspirates.

- Complete Response: No tumor cells detectable by routine morphology on 2 consecutive bilateral bone marrow aspirates and biopsies performed at least 3 weeks apart. Normalization of urinary catecholamines or other tumor markers if elevated at study enrollment.
- Progressive Disease:
  - Patients who enroll with neuroblastoma in bone marrow by morphology have progressive disease if there is a doubling in the amount of tumor in the marrow AND a minimum of 25% tumor in bone marrow by morphology. (For example, a patient entering with 5% tumor in marrow by morphology must increase to  $\geq 25\%$  tumor to have progressive disease; a patient entering with 30% tumor must increase to  $> 60\%$ ).
  - Patients who enroll without evidence of neuroblastoma in bone marrow will be defined as progressive disease if tumor is detected in 2 consecutive bone marrow biopsies or aspirations done at least 3 weeks apart.
- Stable Disease: Persistence of tumor in bone marrow that does not meet the criteria for either complete response or progressive disease.

10.5.2 Overall Best Response Assessment

Each patient will be classified according to their “best response” for the purposes of analysis of treatment effect. Best response is determined from the sequence of the objective statuses described in [Section 10.6](#).

10.6 **Best Response (Solid Tumors)**

Two objective status determinations of disease status, by CT or MRI, obtained on two consecutive determinations, separated by at least a 3 week time period, are required to determine the patient’s overall best response. Two objective status determinations of CR before progression are required for best response of CR. Two determinations of PR or better before progression, but not qualifying for a CR, are required for a best response of PR. Two determinations of stable/no response or better before progression, but not qualifying as CR or PR, are required for a best response of stable/no response; if the first objective status is unknown, only one such determination is required. Patients with an objective status of progression on or before the second evaluations (the first evaluation is the first radiographic evaluation after treatment has been administered) will have a best response of progressive disease. Best response is unknown if the patient does not qualify for a best response of progressive disease and if all objective statuses after the first determination and before progression are unknown.

Table 1: Sequences of objective statuses with corresponding best response.

1 st Status	2 nd Status	3 rd Status	Best Response
Progression			Progressive disease
Stable, PR, CR	Progression		Progressive disease

Unknown	Progression		Progressive disease
Stable	Stable	Progression	Stable
Stable, Unknown	PR, CR	Progression	Stable
Stable, Unknown	Unknown	Progression	Unknown
PR	PR	Progression	PR
PR	CR	Progression	PR
PR, CR	Unknown	Progression	Unknown
CR	CR	Progression	CR
Unknown	Stable	Progression	Stable

Table 2: Overall Response for Patients with Neuroblastoma and Measurable Disease

CT/MRI	MIBG	Bone Scan	Bone Marrow	Catechol	Overall
PD	Any	Any	Any	Any	PD
Any	PD	Any	Any	Any	PD
Any	Any	PD	Any	Any	PD
Any	Any	Any	PD	Any	PD
SD	CR/PR/SD	Non-PD	Non-PD	Any	SD
PR	CR/PR	Non-PD	Non-PD	Any	PR
CR/PR	PR	Non-PD	Non-PD	Any	PR
CR	CR	Non-PD	Non-PD	Elevated	PR
CR	CR	CR	CR	Normal	CR

## 10.7 Response Criteria for Patients with CNS Tumors

### 10.7.1 Selection of Target and Non-Target Lesions

For most CNS tumors, only one lesion/mass is present and therefore is considered a “target” for measurement/follow up to assess for tumor progression/response. If multiple measurable lesions are present, up to 5 should be selected as “target” lesions. Target lesions should be selected on the basis of size and suitability for accurate repeated measurements. All other lesions will be followed as non-target lesions. The lower size limit of the target lesion(s) should be at least twice the thickness of the slices showing the tumor to decrease the partial volume effect (e.g., 8 mm lesion for a 4 mm slice).

Any change in size of non-target lesions should be noted, though does not need to be measured.

